Name of Person Collecting Data: _____

Signature of Person Collecting Data: _____

Date: _____

I. Urine Creatinine and Urine Albumin

III. Method Comparison Study Protocol

Protocol based on the following guidance documents:

Clinical & Laboratory Standards Institute (CLSI). *Method Comparison and Bias Estimation Using Patient Samples; Approved Guideline – Second Edition. EP9-A2.*

Purpose

This protocol is designed to investigate how Allegro results compare to a recognized central laboratory reference method. These studies are important in order to establish the relationship between the Allegro System and the reference method with respect to statistical correlation and measurement bias. This protocol is designed and recommended for the Allegro System.

Background

Good practice dictates that the performance of medical devices such as the Allegro System be verified before the conductance of clinical studies. Verification studies include: method comparisons to determine how the results of the Allegro Systems compare to a recognized reference method, studies of imprecision to determine the reproducibility of the various tests available on the Allegro, and to determine the analytical trueness of the Allegro measurements. The protocol below describes how to conduct a method comparison (Allegro vs. Reference Method).

Materials Needed

- Nova Biomedical Allegro
- Allegro Kidney Function Cartridges
- Nova Biomedical Allegro Quality Control (QC) Solution
- Reference Analyzer and reagents
- 2mL plastic tubes for decanting urine samples
- Plastic 2mL disposable pipettes
- Full range of adjustable pipettes and tips
- If required appropriate Spiking stock solutions

Important Factors to Consider

Tests: Urine Creatinine and urine Albumin

Sample Type: Fresh random urine

Sample Size: 25 μ L

Time per UABCR: 7 mins

Linear Range of Operation: 15-500 mg/dL (13.0-44.2 mmol/L)

Linear Range of Operation for Urine Albumin: 3-300 mg/L

Expected Normal Values

Urine Creatinine: For a random urine sample, >12 Years Male 20-370 mg/dL (1.8- 32.7 mmol/L), >12 Years Female 20 – 320 mg/dL (1.8-28.3 mmol/L)

Urine Albumin: For a random urine sample, normal values are typically 0 to 30 mg/L

Control Levels:

The Allegro supports two levels of controls. The following are suggested ranges for each parameter and level:

Urine Albumin and Creatinine:

Low Level Target:	Urine Albumin ~50 mg/L	Creatinine ~85mg/dL (~8 mmol/L)

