High Level Target:	Urine Albumin ~180 mg/L	Creatinine ~220 mg/dL (~20 mmol/L)

Please note that urine creatinine and urine Albumin are processed at the same time and can be run in both channels

Procedure

1. Fill out the requested information (Allegro serial numbers, cartridge lot numbers, QC lot numbers, QC ranges) on the provided Data Sheets (see Appendix).
2. Perform quality control runs on the Allegro being evaluated and the reference analyzer. Record the results for all systems on the Data Sheet and make sure the results are within the manufacturer's control range. **Proceed with testing only if all control results are within range.**
3. 40-50 fresh (within 24hrs) discarded random urine samples should be collected and run in duplicate on Allegro. Again spiking with creatinine spiking solutions and human Albumin may be required to cover the measuring range.
4. Ensure adequate mixing before analysis.
5. Samples should be analysed promptly on the reference analyser.
7. Cartridges are stored at 4° each cartridge requires 10-15 mins warm up time so consider this requirement when planning study needs.
8. Analyse all samples in duplicate on the Allegro using the same channel to reduce variability
9. Collect, Review and collate data.
10. Total Analysis Time: 7 mins x 80-100 =560 -700 mins. Approx. 9.3 – 11.6 hrs plus preparation time
11. To reduce analysis time consider running samples in singles or perhaps less samples in duplicate whichever best suits site

Data Analysis

As part of this study paired urine creatinine and urine Albumin measurements will be collected. Analysis of accuracy is based on pairing individual results from the Allegro with the corresponding reference analyser measurement and calculating the difference (bias). Scatter plots and linear regression analysis are appropriate tools to assess the relationship between the Allegro results and the reference analyzer. Moreover Bland-Altman plots can be used to assess the bias relative to the range of urine creatinine and urine Albumin concentrations studied. Investigators are referred to organizations such as CLSI and the International Standards Organization (ISO) which offer published acceptance criteria [1, 2]. The validity of the conclusions is dependent on experimental design, chiefly number of samples, the distribution of results, and the calibration of the reference analyzer.

Data Review

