77						
78						
79						
80						
81						
82						
83						
84						
85						
86						
87						
88						
89						
90						
91						
92						
93						
94						
95						
96						
97						
98						
99						
100						

Name of Person Collecting Data: _____
Signature of Person Collecting Data: _____
Date: _____

1. Urine Creatinine and Urine Albumin Summary Report Template

Urine Creatinine and Urine Albumin Summary Report

Date:

Report Author:

Study Site:

Study Site Principal Investigator/Department:

Materials and Methods

See Protocols I-IV. *Any deviations from protocol should be noted here.*

Summary of Results

I. Precision Studies

Table 1. Urine Creatinine Within-Day Precision for Allegro

	Low Urine Creat	Mid Urine Creat	High Urine Creat
Mean mg/dL or mmol/L			
Standard Deviation			
%CV			
N			
Matrix: Urine			

Table 2. Urine Albumin Within-Day Precision for Allegro

	Low Urine Urine Albumin	Mid Urine Urine Albumin	High Urine Urine Albumin
Mean mg/L or g/L			
Standard Deviation			
%CV			
N			
Matrix: Urine			

Table 3. **Urine Creatinine Between-Day** Precision for Allegro

	Low Urine Creat	Mid Urine Creat	High Urine Creat
Mean mg/dL or mmol/L			
Standard Deviation			
%CV			
N			
Matrix: Urine			

Table 4. **Urine Albumin Between-Day** Precision for Allegro

	Low Urine Urine Albumin	Mid Urine Urine Albumin	High Urine Urine Albumin
Mean mg/L or g/L			
Standard Deviation			
%CV			
N			
Matrix: Urine			

II. Method Comparison

Table 7. **Summary of Linear Regression Analysis Results** Urine creatinine and Urine Albumin for the Allegro

	Urine Creat	Urine Albumin
Slope		
y-intercept (mg/dL)		
R ²		
N		
Urine Creat Range mg/dL or mmol/L		
Urine Albumin Range mg/L or g/L		

Table 8. Summary of Bland-Altman Results

	Urine Creat	Urine Albumin
--	-------------	---------------

Mean Bias (mg/dL)		
95% Limits of Agreement		
Lower		
Upper		
Urine Creat Range mg/dL or mmol/L		
Urine Albumin Range mg/L or g/L		

Summary Findings

Allegro demonstrated

This report has been reviewed and approved by:

Signature of Study Site Principal Investigator

Date

Signature of MASA Director

Date

2. HbA1c

I. Within Day Precision Study Protocol

Protocol based on:

Clinical & Laboratory Standards Institute (CLSI). *Evaluation of Precision Performance of Quantitative Measurement Methods; Approved Guideline – Second Edition*. EP5-A2.

Purpose

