This protocol is designed to investigate how Allegro results compare to a recognized central laboratory reference method. These studies are important in order to establish the relationship between the Allegro System and the reference method with respect to statistical correlation and measurement bias. This protocol is designed and recommended for the Allegro System.

Background

Good practice dictates that the performance of medical devices such as the Allegro System be verified before the conductance of clinical studies. Verification studies include: method comparisons to determine how the results of the Allegro Systems compare to a recognized reference method, studies of imprecision to determine the reproducibility of the various tests available on the Allegro studies to determine the analytical trueness of the Allegro measurements. The protocol below describes how to conduct a method comparison (Allegro vs. Reference Method).

Materials Needed

- Nova Biomedical Allegro
- Allegro Lipid Cartridges
- Nova Biomedical Allegro Lipid Quality Control (QC) Solution
- Reference Analyzer and reagents
- 2mL plastic microcentrifuge tubes for decanting Na heparin or Li heparin samples
- Plastic 2mL disposable pipettes
- Full range of adjustable pipettes and tips
- If required appropriate Spiking stock solutions

Important Factors to Consider

Tests: Total Cholesterol, Triglycerides, HDL Cholesterol

Sample Type: Subject to change but to date:

- Capillary whole blood (from finger stick)
- Venous whole blood with anticoagulants Na heparin; Li heparin
- Venous plasma with anticoagulants Na heparin; Li heparin
- Serum

Sample Size: 5 μ L

Time per Lipid: 10 mins

Linear Range of Operation for Total Cholesterol: 100-450 mg/dL (2.59-11.64 mmol/L)

Linear Range of Operation for Triglyceride: 50-600 mg/dL (0.56-6.76 mmol/L)

Linear Range of Operation for HDL Cholesterol: 20-100 mg/dL (0.52- 2.59 mmol/L)

Please note that all parameters are processed at the same time.

Normal Values:

Total Cholesterol: Desirable is below 200 mg/dL (<5.17 mmol/L)

Triglycerides: Desirable is below 150 mg/dL (<1.69 mmol/L)

HDL Cholesterol: Desirable is 60 mg/dL and above (> 1.55 mg/dL)

Control Levels:

The Allegro supports two levels of controls. The following are suggested ranges for each parameter and level:

	Total Cholesterol	Triglycerides	HDL Cholesterol
Low Level Target:	~ 170 mg/dL (~4.40 mmol/L)	~150 mg/dL (~1.69 mmol/L)	~40 mg/dL (~1.04 mmol/L)

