High Level Target:	~ 240 mg/dL (~6.21 mmol/L)	~300 mg/dL (~3.39 mmol/L)	~60 mg/dL (1.55 mmol/L) (~1.55 mmol/L)

Procedure

1. Fill out the requested information (Allegro serial numbers, cartridge lot numbers, QC lot numbers, QC ranges) on the provided Data Sheets (see Appendix).
2. Perform quality control runs on the Allegro being evaluated and the reference analyzer. Record the results for all systems on the Data Sheet and make sure the results are within the manufacturer's control range. **Proceed with testing only if all control results are within range.**
3. 40-50 freshly collected/discarded whole blood venous, Na or Lithium heparin samples should be selected, that if possible, cover the analytical range across all analytes. Again spiking with appropriate spiking solutions may be required to completely cover the analytical range.
4. Ensure adequate mixing before analysis.
5. Analyse all samples in duplicate on the Allegro.
6. Samples should be spun down promptly (plasma) and then be analysed on the reference analyser.
7. Cartridges are stored at 4° each cartridge **the lipids cartridge is only stable at RT for 1 hour**
8. Run all samples in duplicate Allegro, the Lipids cartridge can only be run in the 660nm channel which is on the left hand side of the analyser.
9. Collect, Review and collate data.
10. Total Analysis Time: 10 mins x 80-100 = 800-1000 mins. Approx. 13.3 – 16.6 hrs plus preparation time
11. To reduce analysis time consider running samples in singles or perhaps less samples in duplicate whichever best suits site

Data Analysis

As part of this study paired total cholesterol, triglycerides and HDL cholesterol measurements will be collected. Analysis of accuracy is based on pairing individual results from the Allegro with the corresponding reference analyser measurement and calculating the difference (bias). Scatter plots and linear regression analysis are appropriate tools to assess the relationship between the Allegro results and the reference analyzer. Moreover, Bland-Altman plots can be used to assess the bias relative to the range of urine creatinine and urine Albumin concentrations studied. Investigators are referred to organizations such as CLSI and the International Standards Organization (ISO) which offer published acceptance criteria [1, 2]. The validity of the conclusions is dependent on experimental design, chiefly number of samples, the distribution of results, and the calibration of the reference analyzer.

Data Review

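### Tables 8 and 12 give one absolute mean bias and one pair of 95% limits per analyte over wide ranges; if error rises with level, those limits fit neither end (minor, cheap to improve)

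*Protocol*

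**What the plan says.** The Data Analysis text of 1.III (urine creatinine and albumin) sets the scale: "Analysis of accuracy is based on pairing individual results from the Allegro with the corresponding reference analyser measurement and calculating the difference (bias". Section 3.III (lipids) repeats this: "pairing individual results from the Allegro with the corresponding reference analyser measurement and calculating the difference (bias". Neither section names a percent or log scale.

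The report templates follow suit. Table 8 (kidney) and Table 12 (lipid) each have a row headed "Mean Bias (mg/dL", one lower and one upper 95% limit per analyte, and rows for the concentration range. The limit rows carry no unit. In Table 8 the mg/dL label also covers the albumin column, although the data sheets record albumin in mg/L or g/L.

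The linear ranges are wide. Section 1.III has "Linear Range of Operation for Urine Albumin: 3-300 mg/L" and, for creatinine, "Linear Range of Operation: 15-500 mg/dL"; section 3.III has "Linear Range of Operation for Triglyceride: 50-600 mg/dL". Total cholesterol (100-450 mg/dL) and HDL (20-100 mg/dL) are narrower. Samples are meant to span the range. For urine: "Again spiking with creatinine spiking solutions and human Albumin may be required to cover the measuring range". Section 3.III step 3 says much the same for lipids, where possible.

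The plot that would show how differences behave across the range is permitted, not required: "Moreover Bland-Altman plots can be used to assess the bias relative to the range of urine creatinine and urine Albumin concentrations studied".

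**The concern.** A single absolute pair of limits describes agreement properly only if the spread of the differences is about the same at every level. Over a 12- to 100-fold range that is a strong assumption. The protocol itself works on relative scales elsewhere: precision is summarised as %CV, and section 3.II states lipid accuracy expectations as 3% or 5% of target. This makes rising error plausible, but does not prove it.

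If error does rise with level, a reader of Table 8 would see agreement that looks too loose near 30 mg/L, the upper end of normal albumin, and too tight near 300 mg/L. The signed report may be used to document verification before clinical studies, so its summary should be readable at the levels that matter.

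The mg/dL label on albumin bias is a separate, unconditional slip. Since 1 mg/dL is 10 mg/L, a bias entered in the wrong unit is out by a factor of ten.

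**Working it through.** The protocol states no limits of agreement, SD or CV, so there is no figure to reproduce. The check asks how far pooled absolute limits would be off under stated assumptions.

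**Inputs from the protocol.** Fold ranges: albumin 300/3 = 100; creatinine 500/15 = 33; triglyceride 600/50 = 12; HDL 100/20 = 5; total cholesterol 450/100 = 4.5. Section 1.I gives albumin as 5-300 mg/L, which is 60-fold. The creatinine figure uses the mg/dL range. The printed lower limit of 13.0 mmol/L does not fit the upper pair: 15 × 44.2/500 = 1.33 mmol/L.

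**Assumptions.** Zero mean bias. Levels spread between log-uniform and uniform over lo to hi. SD of the difference proportional to √(c² + x²), where c = 0 is proportional error and c = 0.25 × hi is mixed error (constant and proportional parts equal at a quarter of the upper limit).

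**Formulas.**
- E[x²] = (hi² − lo²)/(2 ln(hi/lo)) for log-uniform levels, and (hi³ − lo³)/(3(hi − lo)) for uniform levels.
- Ratio of pooled to needed width at level x: r = √((c² + E[x²])/(c² + x²)).
- Coverage at x: 2Φ(1.96 r) − 1. The CV cancels.

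**Albumin 3-300 mg/L, proportional error.** Log-uniform: E[x²] = 89,991/9.210 = 9,771, root 98.8. At 300 mg/L, r = 98.8/300 = 0.33 and coverage is 48%. Uniform: root 174.1, r = 0.58, coverage 74%. At 30 mg/L, r = 98.8/30 = 3.3 to 174.1/30 = 5.8.

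**Albumin, mixed error (c = 75).** At 300 mg/L coverage is 57-77%. At 30 mg/L the limits are 1.5 to 2.3 times too wide. Starting at 5 mg/L instead of 3 changes little: 51-75% at the top under proportional error.

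Coverage of nominal 95% limits at the top of the range (log-uniform to uniform levels):

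| Analyte | Full range, proportional | Full range, mixed | Span of the precision targets only, proportional |
|---|---|---|---|
| Albumin | 48-74% | 57-77% | 58-75% (10-200 mg/L) |
| Creatinine | 54-75% | 61-77% | 58-76% (25-450 mg/dL) |
| Triglyceride | 62-76% | 67-79% | 79-83% (100-300 mg/dL) |
| HDL | 72-79% | 75-81% | 85-87% (40-80 mg/dL) |
| Total cholesterol | 73-80% | 76-82% | 81-84% (150-400 mg/dL) |

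With constant SD, r = 1 and coverage is 95% everywhere.

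**Would percent limits alone repair this?** Simulation: 4,000 studies, 45 samples, albumin 3-300 mg/L, percent taken of the true level. Under proportional error, percent limits cover about 94% at every level. Under mixed error (log-uniform / uniform) their width is 3.0 / 0.9 times what is needed at 30 mg/L and 7.8 / 2.3 times at 300 mg/L, and at 3 mg/L they cover only 46% / 15%. So they do not.

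**Limits from a regression.** In the same simulation, the differences were regressed on level, then the absolute residuals on level, and the fitted value was multiplied by 1.96√(π/2). Under mixed error the width is 1.05 / 0.93 of what is needed at 30 mg/L and 0.84 / 0.94 at 300 mg/L. At 3 mg/L coverage is 89% / 70% under mixed error and 71% / 48% under proportional error, so the very bottom remains weak.

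**The case against.** The defect is conditional. A pooled mean difference with 95% limits is the standard Bland-Altman summary, and with constant SD it is right. This stands, and it limits the point. A reader might infer that the limits in Tables 8 and 12 will be wrong; the documents do not support that, because they give no information on error by level.

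The protocol also offers partial help. Tables 7 and 11 report slope and intercept, the precision tables report SD and %CV by level, and 1.III warns that validity depends on how the results are distributed. But slope and intercept describe mean bias, not the spread of differences, and the precision tables describe the Allegro's own repeatability, not its disagreement with the reference.

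It could be said that the scale belongs in a SAP that is not shown. The report templates are in this protocol, however, and they fix an absolute unit.

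Full-range sampling is not assured: spiking is optional and lipid coverage is only sought where possible. That stands. Over the narrower precision-target span the triglyceride effect shrinks to 79-83%, while albumin and creatinine hardly change.

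Finally, a reader might infer that percent limits should replace the absolute ones, or that a wrong verification decision follows. Neither is supported. Percent limits are right only under proportional error, and no acceptance rule in the protocol uses these tables.

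**Conclusion.** The point holds as a minor, inexpensive improvement. The protocol fixes one absolute bias and one pair of limits per analyte over ranges that it means to span. If error rises with level, those limits are too wide at low levels and too narrow at the top, with about 48-77% coverage at 300 mg/L albumin under proportional or mixed error. Creatinine is close behind and triglyceride is affected less; total cholesterol and HDL matter least. These figures rest on an assumed error model, an assumed spread of samples and zero mean bias. The harm is a summary that can mislead, not lost data, since the paired results stay on the data sheets. The albumin unit label in Table 8 is wrong whatever the error model.

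**What to change.** In Tables 8 and 12:
- Keep the absolute mean bias and limits.
- Add mean bias and 95% limits for the percent difference, with the pair mean as the denominator stated in advance.
- Add 95% limits at stated low, medium and high levels, for example the protocol's own precision targets, from a pre-specified regression of the absolute differences on level. Report all of these always, with no data-driven choice of scale.
- Put the correct unit on every row and column, in particular mg/L (or g/L) for albumin bias and its limits. The intercept row in Table 7 has the same mg/dL label and needs the same correction.

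In the Data Analysis text of 1.III and 3.III, require the difference-versus-level plot in the report.

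Cost: a few more rows and some analysis work on the same pairs, with no new samples. The report should say that percent limits are unreliable at the very bottom of the albumin range unless error is proportional, and that the regression limits are weak there too.

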This protocol is recommended and designed by Nova Biomedical to investigate the within-day precision of whole blood HbA1c measurements on the Allegro system.

Materials Needed

- Nova Biomedical Allegro
- Allegro Glycaemic Control Cartridges
- Nova Biomedical Allegro Quality Control (QC) Solution
- Reference Analyzer and reagents
- 2mL plastic microcentrifuge tubes for decanting EDTA samples
- Plastic 2mL disposable pipettes
- Full range of adjustable pipettes and tips

- Appropriate Spiking stock solutions

Important Factors to Consider

Tests: HbA1c

Sample Type:

- Capillary blood (from finger stick)
- Fresh venous whole blood with anticoagulants ethylenediamine tetra-acetic acid (EDTA); Li heparin; Na heparin

Sample Size: 1.5 µL

Time per HbA1c: 6.5 mins

Linear Range of Operation for HbA1c: 4-15% (20.2 - 140.4 mmol/L)

Potential Interferences

HbA1c measurement is not affected by Hb variants: HbAc, HbAD, HbAE, HbF, HbAG and HbAS

Control Levels:

The Allegro supports two levels of controls. The following are suggested ranges for each parameter and level:

HbA1c:

Low Level Target: ~5% (31.1 mmol/mol)

High Level Target: ~10% (85.5 mmol/mol)

Normal Values

HbA1c: - A normal non-diabetic HbA1c is <5.5% (36mmol/mol). In diabetes about **6.5%** (48 mmol/mol) is good.

Procedure

1. Fill out the requested information (Allegro serial numbers, cartridge lot numbers, QC lot numbers, QC ranges) on the provided Data Sheets (see Appendix).
2. Perform quality control runs on the Allegro being evaluated and the reference analyzer. Record the results for all systems on the Data Sheet and make sure the results are within the manufacturer's control range. **Proceed with testing only if all control results are within range.**
3. Using aliquoted venous EDTA whole blood identify three levels low, medium and high.
4. Suggested concentrations for low, medium and high samples: -

	HbA1c
Low Target	~5% (31.1 mmol/mol)
Medium Target	~7% (53 mmol/mol)

High Target ~10% (85.8 mmol/mol)

5. Ensure adequate mixing before analysis.
6. Cartridges are stored at 4° each cartridge the HbA1c cartridge can be used cold
7. Run each Level 10 times on Allegro, the HbA1c cartridge can only be run in the 600nm channel which is on the right hand side of the analyser.
8. Collect, review and collate data.

Total Analysis Time: 6.25 mins x 10 = 62.5 mins per level. 187.5 mins for all levels. Approx. 3.15 hrs plus preparation time

Data Analysis

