The within-run precision of the Allegro be assessed by calculating the % coefficient of variation (%CV) from the mean and standard deviation from the replicate measurements. Acceptability criteria are determined by the medical director and/or institution. Investigators are referred to organizations such as CLSI and the International Standards Organization (ISO) which offer published acceptance criteria [4].

Data Review

This data will be summarized in a final report which will also include an assessment of the accuracy. This report should be reviewed by the study site principal investigator. Results of this laboratory evaluation can be used to document verification of Allegro performance prior to the conductance of clinical studies.

References

1. Clinical & Laboratory Standards Institute (CLSI). *Evaluation of Precision Performance of Quantitative Measurement Methods; Approved Guideline – Second Edition*. EP5-A2.

Appendix 1

Within-Day Precision Study Data Collection Sheet

Hospital Name: _____ Date of Study: _____

System Operator(s): _____

Reference Analyzer _____

Level 1 HbA1c

Reference Analyzer Result % mmol/mol _____

	System Name							
	System Serial #							
	Cartridge Lot #							
Low QC	Range:							
High QC	Range:							
	Replicate #	HbA1c						

		% or mmol/Mol						
	1							
	2							
	3							
	4							
	5							
	6							
	7							
	8							
	9							
	10							

Level 2 HbA1c

Reference Analyzer Result % or mmol/mol _____

	System Name							
	System Serial #							
	Cartridge Lot #							
Low QC	Range:							
High QC	Range:							
	Replicate #	HbA1c % or mmol/mol						
	1							
	2							
	3							
	4							
	5							
	6							
	7							
	8							

	9							
	10							

Level 3 HbA1c

Reference Analyzer Result % or mmol/mol _____

	System Name							
	System Serial #							
	Cartridge Lot #							
Low QC	Range:							
High QC	Range:							
	Replicate #	HbA1c % or mmol/mol						
	1							
	2							
	3							
	4							
	5							
	6							
	7							
	8							
	9							
	10							

Name of Person Collecting Data: _____

Signature of Person Collecting Data: _____

Date: _____

2. HbA1c

II. Between-Day Precision Study Protocol

Protocol based on:

Clinical & Laboratory Standards Institute (CLSI). *Evaluation of Precision Performance of Quantitative Measurement Methods; Approved Guideline – Second Edition*. EP5-A2.

Purpose

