1. Clinical & Laboratory Standards Institute (CLSI). *Method Comparison and Bias Estimation Using Patient Samples; Approved Guideline – Second Edition. EP9-A2.*

Appendix 4

Method Comparison Data Collection Sheet (Case Report Form)

Study Site: _____ Date of Study: _____

System Operator(s): _____

Specimen Type (Venous EDTA Whole Blood) _____

Reference Analyzer _____

	System Name		
	System Serial #		
	Cartridge Lot #		
Low QC	Range:		
High QC	Range:		
Specimen ID	Reference Analyzer Result % or mmol/mol	HbA1c result % or mmol/mol	HbA1c result % or mmol/mol
1			
2			
3			
4			
5			
6			
7			
8			
9			
10			
11			
12			
13			
14			
15			
16			
17			
18			
19			
20			
21			
22			
23			
24			
25			
26			
27			
28			
29			
30			

Specimen ID	System Name		
	System Serial #		
	Cart Lot #		
	Reference Analyzer Result % or mmol/mol	HbA1c result % or mmol/mol	HbA1c result % or mmol/mol
31			
32			
33			
34			
35			
36			
37			
38			
39			
40			
41			
42			
43			
44			
45			
46			
47			
48			
48			
49			
50			
51			
52			
53			
54			
55			
56			
57			
58			
59			
60			
61			
62			
63			
64			
65			
66			
67			
68			
69			
70			
71			
72			
73			

	System Name		
	System Serial #		
	Cart Lot #		
Specimen ID	Reference Analyzer Result % or mmol/mol	HbA1c result % or mmol/mol	HbA1c result % or mmol/mol
74			
75			
76			
77			
78			
79			
80			
81			
82			
83			
84			
85			
86			
87			
88			
89			
90			
91			
92			
93			
94			
95			
96			
97			
98			
99			
100			

Name of Person Collecting Data: _____

Signature of Person Collecting Data: _____

Date: _____

2. HbA1c

Summary Report Template

HbA1c Summary Report

Date:

Report Author:

Study Site:

Study Site Principal Investigator/Department:

Materials and Methods

See Protocols I-IV. *Any deviations from protocol should be noted here.*

Summary of Results

I. Precision Studies

Table 1. **HbA1c Within-Day** Precision for Allegro

	Low HbA1c	Mid HbA1c	High HbA1c
Mean % or mol/mol			
Standard Deviation			
%CV			
N			
Matrix			

Table 2. **HbA1c Between-Day** Precision for Allegro

	Low HbA1c	Mid HbA1c	High HbA1c
Mean % or mol/mol			
Standard Deviation			
%CV			
N			
Matrix			

II. Method Comparison

Table 5. Summary of Linear Regression Analysis Results HbA1C for Allegro

HbA1c	
Slope	
y-intercept (% or mmol/mol)	
R ²	
N	
HbA1c Range % or mmol/mol	

Table 6. Summary of Bland-Altman Results

HbA1c	
Mean Bias (% or mmol/mol)	
95% Limits of Agreement	
Lower	
Upper	
HbA1c (% or mmol/mol)	

Summary Findings

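### Does letting a site record HbA1c in either % or mmol/mol make the %CV precision result unreliable?

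*Protocol*

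**What the plan says.** Sections 2.I and 2.II of the Protocol (HbA1c, within-day and between-day precision) name one statistic. Precision is "assessed by calculating the % coefficient of variation (%CV) from the mean and standard deviation" of the replicates. The same Data Analysis paragraphs leave the pass mark open: "Acceptability criteria are determined by the medical director and/or institution". They also point the investigator to published criteria. No numerical CV limit for HbA1c appears anywhere in the document.

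The recording unit is optional. The Level 1 data sheet in 2.I is headed "HbA1c % or mmol/Mol", the between-day sheets in 2.II offer the same choice, and the mean row of summary Tables 1 and 2 reads "Mean % or mol/mol". The SD and %CV rows below it carry no unit.

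The Protocol prints several values in both units. The low target in 2.I is "5% (31.1 mmol/mol" and the high sample target is "10% (85.8 mmol/mol". The control list in the same section prints a slightly different figure, "High Level Target: ~10% (85.5 mmol/mol". The working range is "Linear Range of Operation for HbA1c: 4-15% (20.2 - 140.4 mmol/L", where the last unit is evidently a slip for mmol/mol.

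**The concern.** A CV is unchanged when every result is multiplied by a constant, but not when a constant is also added or subtracted. The lipid sections offer mg/dL or mmol/L, which differ only by a factor, so the choice there is harmless. The HbA1c section uses the same either-unit layout for two scales that are not proportional. The single precision statistic named for HbA1c therefore takes two values for one set of replicates, and the plan does not say which one a limit refers to.

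The reports are meant to document verification of the analyser before clinical studies. If a limit in one unit were set against a CV in the other, an acceptable device could fail or a poor one could pass. Two sites using different units would also print CVs that cannot be compared directly. Because the factor changes with concentration, a constant relative imprecision in % would appear to worsen at low levels in mmol/mol.

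**Working it through.** The Protocol gives no HbA1c CV, limit or precision calculation, so there is no stated figure to reproduce. The check is how far apart the two CVs are, and whether the report still allows a reader to tell them apart.

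**Inputs (Protocol 2.I).** 5% = 31.1, 7% = 53 and 10% = 85.8 mmol/mol (Procedure step 4); 10% = 85.5 (Control Levels); 4% = 20.2 and 15% = 140.4 (linear range).

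**Conversion line.** From the 5% and 10% targets:
- slope = (85.8 − 31.1)/(10 − 5) = 10.94
- intercept = 31.1 − 5 × 10.94 = −23.6
- check at 7%: 10.94 × 7 − 23.6 = 52.98, against the printed 53

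From the range ends: slope = (140.4 − 20.2)/(15 − 4) = 10.93, intercept −23.5. The offset is therefore not an artefact of one rounded pair.

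**Ratio of CVs.** The SD is multiplied by the slope and the mean moves along the line, so CV(mmol/mol)/CV(%) = slope × mean(%) / mean(mmol/mol).

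| Level | Calculation | Ratio | With 85.5 at 10% (slope 10.88) |
|---|---|---|---|
| 5% | 10.94 × 5/31.1 | 1.76 | 1.75 |
| 7% | 10.94 × 7/53 | 1.44 | 1.44 |
| 10% | 10.94 × 10/85.8 | 1.28 | 1.27 |

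As an assumed example, a 2.0% CV in % units becomes 3.5%, 2.9% and 2.6% in mmol/mol. If 2.II uses the two control solutions it suggests, only the 5% and 10% rows apply between days.

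**Lipid contrast.** Total cholesterol 100-450 mg/dL = 2.59-11.64 mmol/L: slope (11.64 − 2.59)/350 = 0.02586, and 0.02586 × 100/2.59 = 1.00 and 0.02586 × 450/11.64 = 1.00. The effect is specific to HbA1c.

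**When a verdict could change.** For a limit L applied without regard to unit, the two units disagree only if the CV in % units lies between L/ratio and L: 0.57L to L at 5%, 0.69L to L at 7%, 0.78L to L at 10%. Outside these bands the verdict is the same.

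**Can the reader tell the units apart?** The stated working range is 4 to 15 in % and 20.2 to 140.4 in mmol/mol. These intervals do not overlap, so any mean within range identifies its own unit even if nobody strikes out the unused one.

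**Can the other CV be recovered?** Yes, from the mean and SD printed in the same column. Taking the 5% level and the 2.0% example, the SD in % is 0.02 × 5 = 0.10, which is 0.10 × 10.94 = 1.094 mmol/mol, and the reported CV is 1.094/31.1 = 3.5%. Adding the offset back gives 1.094/(31.1 + 23.6) = 1.094/54.7 = 2.0%.

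**The row label.** Printing mol/mol for mmol/mol is a factor of 1,000 with no offset. It leaves the CV unchanged and is clerical.

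**The case for a change.** The strongest case for a change is that the either-unit rule is written into the Protocol's own forms, so it is a choice the document makes and not merely something left unsaid. The factors are large, the bands in which a verdict could differ are wide, the lipid layout invites a reader to assume that CV does not depend on the unit, and one sentence would settle the matter.

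Much of this stands. The ratios are right and follow from the Protocol alone. Anyone comparing HbA1c CVs across sites, or with a published limit, should check the unit first.

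What does not stand is the step from there to a fault. Allowing either unit produces no incorrect number, because a CV in mmol/mol is as legitimate as one in %. Harm needs three things together: a limit in one unit, data in the other, and a CV inside the band. The Protocol sets no limit, so it cannot have set one in the wrong unit. It leaves the limit to the same institution that chooses the recording unit. Whether the published criteria it mentions already name a unit cannot be judged from this document. Tying a CV limit to its unit is the kind of detail that a statistical analysis plan or the site's own verification plan supplies, and the former is not at hand.

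**Conclusion.** The observation is correct but calls for no change. HbA1c %CV is 1.76, 1.44 and 1.27 to 1.28 times larger in mmol/mol than in % at the 5%, 7% and 10% levels. The Protocol nevertheless contains no CV, limit or conversion that this makes wrong, and its summary tables hold what is needed to identify the unit and recompute the CV. The remaining gap, which unit a limit refers to, is one that a site fills in the ordinary course of setting the limit. Only one of the six analytes is affected, and the method comparison in 2.III needs no more than both methods being reported in one unit.

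This rests on two assumptions: that a site keeps to one unit throughout a study, and that it expresses its limit in that unit. If a site did mix them, the bands above show when the conclusion would be at risk.
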